6.2.4 Treatment Exposure and Drug Accountability

6.2.4.1 Treatment Exposure

Exposure will be summarized for the ITT population and SAF population. Subjects are instructed to bring their study medication and all empty packaging to the clinic visit. Cumulative treatment exposure per subject will be calculated as sum of all dosage of treatment consumed. Time on treatment (in days) will be calculated per subject as the number of days of study medication intake during the trial. This will be calculated as:

Date of last study medication administration – Date of first study medication administration + 1.

Dosing data will be presented descriptively by treatment group and also presented as subject data listing for the ITT population and Safety population.

6.2.4.2 Accountability/Compliance

Drug compliance will depend upon capsule counts at each visit. Subjects are instructed to bring their study medication and all empty packages to each clinic visit. Compliance will be assessed by capsule counts recorded by each site for each subject. The details of medication used will be recorded and reconciled against expected medication use. Compliance will be calculated as the reported medication used by subject as percentage (%) of expected usage. Summary descriptive statistics will be presented for the number and proportion of subjects non-compliant (< 80% compliant) for safety population.

Extent of compliance of each subject data will be presented in subject listing for the SAF population.

6.2.5 Physical Examination

Physical examination of each subject's major body systems: general appearance, head/eyes/ears/nose/throat, neck, lungs, heart, abdomen, genitourinary, extremities, neurological, skin, and lymphatics and other. Results (normal, abnormal and clinically significant abnormal and not clinically significant) at baseline and post-baseline visits will be tabulated for each body system with the number and percentage of subjects.

All physical examination results will be presented in a subject data listing, including the description of abnormalities.

6.2.6 Medical History (excluding Crohn's disease)

6.2.6.1 Medical History (excluding Crohn's disease)

Pre-existing medical conditions are recorded at screening and at baseline on the medical history eCRF. For each subject, medical history data will be presented in a data listing.

6.2.6.2 Crohn's Disease History

Crohn's disease history is recorded at screening and baseline on the history eCRF. Data will be presented descriptively by treatment group and also presented as data listing for the ITT population.

Final Version 3.0, 05 April 2018

6.2.7 Prior and Concomitant Medications and Steroids

Prior medications will be defined as medications stopped prior to Day 1 of study medication. Concomitant medications include medications taken on or after the first dose of study medication as well as medications that started prior to the first dose of study medication and continued after the first dose of study medication. The following algorithm will be used to define prior and concomitant:

The medication will be assumed to be prior medication if it cannot be definitively shown that the medication did not start or continue during the treatment period.

If the start date or stop date of a medication is partially missing, the date will be compared as far as possible with the date of the start of administration of study drug. The following approach will be taken:

- If the start date of medication is complete and occurs on or after the day of the first dose, the medication will be assumed concomitant. If the start date occurs prior to the first dose date but the end date is on or after the first dose date or the medication is recorded as ongoing, the medication will be considered concomitant.
- If the start day is missing but the start month and year are complete, a medication will only be excluded as being concomitant if the start month/year is before the month/year of study drug administration and if the stop date (either full date, month and year if missing day, or year if missing month and day) is before study drug administration.
- If the start day and month are missing but the start year is complete, a medication will only be excluded as concomitant if the start year is before the year of study drug administration and if the stop date (either full date, month and year if missing day, or year if missing month and day) is before study drug administration.
- If the start date is completely missing and the stop date is prior to first dose or completely missing, the medication will be assumed to be a prior medication.

All prior and concomitant medications recorded on CRF will be mapped to standardized terms using the World Health Organization Drug Dictionary coding system (WHO DD). The Anatomical–Therapeutic–Chemical (ATC) Classification level 2 and preferred term will be used to summarize the data by treatment group. A subject having the same medication more than once will be counted only once in the incidence table for that medication. For each ATC classification and Preferred Term the number and percentage of subjects will be displayed. Summary tables will be presented on SAF population separately for prior medications and concomitant medications by treatment group.

All prior and concomitant medications/treatments will be presented in a data listing with dose, units, frequency, route of administration, indication, start and end dates for the safety population. A separate Steroids use subject listing may be presented providing the steroid coded ATC classification, preferred term, and date.

Any concomitant procedures recorded on CRF will be presented in a data listing with procedure name, date and reason.

6.3 Efficacy Analysis

The efficacy primary analyses will be based on the ITT population as the primary population. Any Supportive/sensitivity analyses may be assessed on subgroup populations of subjects that will be defined for each endpoint as needed for implementing specific sensitivity analysis. Additional analyses as defined in SAP addendum will be performed accordingly as specified.

6.3.1 Primary Efficacy Analysis

The primary efficacy analysis will be performed on ITT population. Sensitivity analyses may be performed on Observed Case (completers only), on subjects with no violation of key inclusion/exclusion criteria (mITT population), and on PP population.

The primary efficacy variable is the proportion of subjects experienced remission week 26, where remission is defined as a subject having a Crohn's Disease Activity Index (CDAI) score of < 150 . Subjects who have a week 26 CDAI measurement ≥ 150 or who do not have a CDAI measurement week 26 will be classified as not achieved remission. The primary analysis will compare the RHB-104 treated group to Placebo treated group on ITT population using Cochran-Mantel-Haenszel (CMH) chi-square test controlling for the stratification variable anti-TNF agents use (yes/no). The null and alternative hypotheses are as follows, where π_R and π_P are the proportion of subjects with remission in the RHB-104 and placebo treated groups, respectively.

Null hypothesis $H_0: \pi_R = \pi_P$

"Proportion (%) of subjects in Remission in RHB-104 Treatment is equal to Proportion (%) of subjects in Remission in Placebo Treatment at week 26"

Alternative hypothesis $H_1: \pi_R \neq \pi_P$

"Proportion of subjects in Remission for RHB-104 Treatment is not equal to Proportion of subjects in Remission for Placebo treatment at week 26"

For each treatment group, descriptive statistics will be presented including the number of observations, proportion (%) of subjects in remission.

The primary analysis will compare RHB-104 group to the placebo group using a two-sided test at the $\alpha = 0.049$ level of significance.

The statistical criterion for primary objective success will be met if the CMH chi-square test p-value comparing the RHB-104 arm with the placebo arm (Higher proportion in RHB-104 than placebo) is less than 0.049 based on a 2-sided test taking into account the pre-specified protocol alpha spent at interim equal to 0.003.

For each treatment group, parameter estimates with 95% confidence interval will be presented including the number of observations and proportion (%) of subjects in remission.

To assess the robustness of the primary results, sensitivity analysis will be performed on mITT and on observed case (only completers with 26 weeks of data). The observed case population will include only subjects that have 26 weeks assessment.

Logistic regression modeling will be implemented as additional exploratory analysis to assess the modifying effect of prognostic baseline characteristics identified prospectively as clinically important baseline factors/variables on the remission outcome in both treatment groups at week 26. This will model a categorical response variable Remission (< 150 CDAI score) at week 26 (yes/no) as a function of treatment, stratification anti-TNF agents (yes/no) use, and treatment-by-baseline clinical factor interaction. The aim is to assess consistence/inconsistence of the treatment differences across each of the pre-defined clinically important baseline characteristics (one-variable-at-a-time). Each prognostic factor will be fitted separately (one-variable-at-a-time) in the model and output results including 95% confidence intervals presented in forest plots showing consistence/inconsistence by treatment group. The following baseline factors are considered prospectively to be potentially clinically important:

- Baseline serum inflammation marker: C-reactive protein (Normal/High)
- Baseline stool inflammation marker: Fecal calprotectin (Normal/High)
- Baseline CDEIS score (0-3; >3 score)
- Baseline SES-CD score (0-2; >2 score)
- Baseline IBDQ Score
- Duration of CD
- Prior surgical treatment for CD (yes/no)
- MAP-Test PCR Blood assay (Positive/Negative) Baseline
- MAP-Test Blood culture (Positive/Negative) Baseline
- Gender (male/female)
- Age at first Diagnosis of CD
- Smoking (yes/no)
- Alcohol consumption (yes/no)
- Use of Immunomodulators (yes/no)
- Use of steroids (yes/no)

The continuous variables may be categorized into different classification categories depending on the number of observations and final decisions on categories for each variable will be determined at the time of analysis.

6.3.2 Key Secondary Efficacy Endpoints Analyses

Five key secondary efficacy endpoints of clinical importance are considered for primary inferential claims. Since gate keeping hierarchical sequential testing strategy is required for multiplicity adjustment, any claim on these key secondary efficacy endpoints will be made only if the primary efficacy endpoint parameter meets the criterion for statistical success. The hierarchical sequence hypothesis testing for multiplicity adjustment is summarized in section 6.1.2 above. The hypothesis testing will be done in a sequential manner following the sequential order given in section 6.1.2 with the understanding that any hypothesis test of a subsequent endpoint will be performed only if the test for the preceding endpoint is significant. In other words, the endpoint hypothesis examined earlier serves as gatekeeper.

6.3.2.1 Response week 26

The Response week 26 is defined as the proportion (%) of subjects that experienced reduction from baseline of ≥ 100 in CDAI score. The same statistical analysis strategy as described for the primary endpoint including sensitivity and exploratory analyses will be repeated for the proportion responders (%) at 26 weeks comparing the two treatment groups. Summary parameter estimates generated from the statistical analyses will be presented by treatment group, and will include the number and proportion of subjects achieving response along with the model estimated odds ratio (including 95% confidence interval) and p-value comparing RHB-104 treatment to placebo. The same sensitivity and exploratory analyses as for primary endpoint analysis may be conducted and summarized.

6.3.2.2 Remission week 52

Remission at week 52 will be derived following similar strategy as for the primary endpoint. The subjects in remission will include subjects experienced remission (CDAI < 150 score) at week 26 and also at week 52, and subjects that were non-responders at week 26 but are responders at week 52 (Late responders).

The same statistical methods as used for the primary endpoint will be used for this analysis. The proportion of subjects experienced remission at 52 weeks will be summarized for each treatment group and compared between the two treatments using Cochran-Mantel-Haenszel (CMH) chi-square test. Summary parameter estimates generated from the statistical analyses will be presented by treatment group, and will include the number and proportion of subjects achieving response along with the model estimated odds ratio (including 95% confidence interval) and p-value comparing RHB-104 treatment to placebo. The same sensitivity and exploratory analyses as for primary endpoint analysis may be conducted and summarized.

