2.2.2 Key Secondary Efficacy Endpoints/Variables

Key Secondary efficacy endpoints include the following:

- Proportion of subjects experienced response at week 26, where response is defined as reduction from baseline of ≥ 100 in CDAI score. Subjects who have a change from baseline to week 26 in CDAI score which is not a reduction of ≥ 100 or who do not have a change from baseline to week 26 in CDAI score will be classified as not experienced response.
- Proportion of subjects in remission Week 52, where remission is defined as a subject having a CDAI score of < 150 . Subjects who have a week 52 CDAI measurement ≥ 150 or who do not have a CDAI measurement week 52 will be classified as not achieved remission.
- Proportion of subjects experienced Durable Remission (CDAI score < 150) from week 26 through week 52. Subjects experiencing a CDAI score ≥ 150 at any visit time point assessment between week 26 and week 52 or have no CDAI measurement week 26 or week 52 will be considered not achieved Durable Remission.
- Proportion of subjects in Early Remission week 16, where remission is defined as a subject having a CDAI score of < 150 . Subjects who have a week 16 CDAI score ≥ 150 or who do not have a CDAI measurement week 16 will be classified as not achieved early remission.
- Proportion of subjects in steroid free remission week 52, where remission is defined as a subject having a CDAI score of < 150 . Subjects must be maintained off steroids for 3 weeks in order to be determined to be in steroid free remission, e.g., by week 49.

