6.1.2 Multiplicity and Testing Strategy

Multiplicity issues in statistical inference in this study may arise from repeated tests on several multiple endpoints specified in the protocol. Additionally, the impact of the Type I error probability (α) because of the formal planned interim analysis to be conducted needs to be understood.

The protocol specified α -spending for the planned interim analysis is 0.003. Hypotheses tests at the final analysis will be conducted at significance level of $\alpha = 0.049$. The multiple efficacy tests for the study final analysis will employ a serial sequential gatekeeper strategy to maintain the Type 1 error rate at $\alpha = 0.049$ across two families of analyses that support the primary, and key secondary objectives. The protocol pre-specified strategy is to use a hierarchy of significance tests where each test acts as a gatekeeper to tests below it. The endpoints will be tested in a sequential manner and will follow the sequential order given below starting with Remission ranked 1. Any inferential and hypothesis testing of a subsequent endpoint will be performed only if the test for the preceding endpoint is significant. In other words, the endpoint hypothesis examined earlier serves as gatekeeper. For this study as listed below in sequence of clinical importance, Remission week 26 is first rank (1) and will be tested first followed by Response week 26 (rank 2), followed by Remission week 52 (rank 3), Durable Remission week 26 through week 52 (rank 4), followed by Remission week 16 (rank 5), and followed by Steroid free Remission week 52 (rank 6). Again it is important to note that once one hypothesis is tested and found not to be significant at $\alpha = 0.049$, all subsequent tests will not be performed. The multiplicity adjustment following hierarchal testing procedure comparing RHB-104 with Placebo will only be performed on the following key clinical efficacy endpoints listed in order of clinical importance:

1. Remission (CDAI score < 150) week 26 - Primary Efficacy Endpoint.
Key Secondary Efficacy Endpoints:
2. Response (reduction from baseline of ≥ 100 in CDAI score) week 26.
3. Remission (CDAI score < 150) week 52
4. Durable Remission (CDAI score < 150) from week 26 through week 52 in remission.

5. Remission (CDAI score < 150) week 16
6. Proportion of subjects in steroid free remission week 52 (CDAI score < 150 and no steroids use by week 49).

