This analysis is intended to compare the two treatment groups based on the proportion (%) of subjects achieved Sustained Remission defined as maintaining CDAI score < 150 from week 16 through week 52. Subjects who are not in remission at any visit point assessment between week 16 and week 52 will be considered as non-responders for this analysis. The same statistical method as used for the primary endpoint will be used for this analysis. The proportion (%) of subjects experienced sustained remission will be summarized for each treatment group and compared between the two treatments using Cochran-Mantel-Haenszel (CMH) chi-square test. Summary parameter estimates generated from the statistical analyses will be presented by treatment group, and will include the number and proportion of subjects achieving sustained remission along with the model estimated odds ratio (including 95% confidence interval) and p-value comparing RHB-104 treatment to placebo.

An additional complementary analysis and summary will be presented for the Proportion of subjects that maintained durable remission at least 5 out of the 6 visits assessed (i.e. $\geq 83\%$ of the visits in remission) week 16 through week 52.

6.3.3.3 Response at Week 52

The Response is defined as reduction from baseline of ≥ 100 in CDAI score week 52. The responders will include subjects who were responders week 26 through week 52 and the subjects that were non-responders at week 26 but were responders week 52 (Late Responders).

The same statistical methods as used for the primary endpoint will be used for this analysis. The proportion of subjects experienced response at 52 weeks will be summarized for each treatment

group and compared between the two treatment groups using Cochran-Mantel-Haenszel (CMH) chi-square test.

6.3.3.4 Early Response week 16

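### SAP 6.3.2.2 adds late responders to Week 52 remission without a CDAI <150 condition, which conflicts with 2.2.2 and 6.1.2 and should be reconciled before unblinding

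*SAP*

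**What the plan says.** **Endpoint definition.** SAP 2.2.2 lists "Proportion of subjects in remission Week 52, where remission is defined as a subject having a CDAI score of < 150". It then classes "Subjects who have a week 52 CDAI measurement ≥ 150", and those with no Week 52 measurement, as not in remission. The same section defines response as a fall from baseline of at least 100 CDAI points.

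**Testing hierarchy.** SAP 6.1.2 places "Remission (CDAI score < 150) week 52" third in the fixed sequence. Durable remission, Week 16 remission and Week 52 steroid-free remission follow as ranks 4 to 6, each tested only if the preceding test is significant.

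**Derivation.** SAP 6.3.2.2 opens with "Remission at week 52 will be derived following similar strategy as for the primary endpoint". Its next sentence says whom the remission group will include: first, "subjects experienced remission (CDAI < 150 score) at week 26 and also at week 52"; second, "subjects that were non-responders at week 26 but are responders at week 52 (Late responders". The first group carries the CDAI limit and the second does not.

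**The same phrase elsewhere.** SAP 6.3.3.3, on the 100-point response at Week 52, has nearly identical wording: "the subjects that were non-responders at week 26 but were responders week 52 (Late Responders".

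**The concern.** One alpha-controlled endpoint has two descriptions that need not select the same subjects. 'Response' is a defined term, and 6.3.2.1, immediately above, uses it in the 100-point sense. A programmer working from 6.3.2.2 could therefore apply the 100-point rule to the second group and obtain an endpoint that 2.2.2 would not recognise as remission.

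At stake is the rank 3 test and, through the gatekeeping, whether ranks 4 to 6 are tested at all. If the ambiguity were settled only after unblinding, the choice between two possible results would not have been pre-specified.

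**Working it through.** **Inputs.** Baseline CDAI 220 to 450 (protocol synopsis, inclusion criteria). Remission: CDAI <150 (SAP 2.2.2). Response: fall of at least 100 (SAP 2.2.2). Final two-sided alpha 0.049 (SAP 6.1.2).

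**The plan's own figures.** The documents give no expected rate or power for Week 52 remission. The sample size in 6.1.9 concerns the primary endpoint and is consistent with its statement of at least 80% power. At 162 per arm, 36% against 21%, alpha 0.049:

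- mean proportion (0.21 + 0.36)/2 = 0.285
- SE under the null = √(2 × 0.285 × 0.715/162) = 0.0502
- SE under the alternative = √((0.21 × 0.79 + 0.36 × 0.64)/162) = 0.0495
- power = Φ((0.15 − 1.969 × 0.0502)/0.0495) = 85.0%, or 81.9% with continuity correction

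Nothing in this point changes that calculation.

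**Where response and remission part.** Let B be baseline and C the Week 52 CDAI, in whole points.

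- Response without remission needs 150 ≤ C ≤ B − 100, so B ≥ 250. That covers 450 − 250 + 1 = 201 of the 450 − 220 + 1 = 231 eligible baseline values. C can be as high as 450 − 100 = 350. The 201 of 231 counts possible values, not a share of subjects.
- Remission without response needs B − 99 ≤ C ≤ 149, so B ≤ 248. For example, 220 to 149 is a fall of 71.

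**Two subjects under each reading** (baseline → Week 26 → Week 52):

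| CDAI path | 2.2.2 and 6.1.2 | 6.3.2.2, response as defined | 6.3.2.2, 'responder' read as 'in remission' |
|---|---|---|---|
| 400 → 320 → 290 | Not in remission | Counted: falls of 80, then 110 | Not counted |
| 300 → 180 → 120 | In remission | In neither group: fall of 120 at Week 26 makes a responder, CDAI 180 is not remission | Counted |

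The second path is one the trial expects. SAP section 3 and the protocol's study design both say that Week 26 responders may reach remission later. On the defined-response reading, an exhaustive list also omits late remitters whose fall is under 100 points.

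**The generic reading.** If 'responder' means 'in remission', the groups are (remission at 26 and at 52) and (no remission at 26, remission at 52). Their union is everyone in remission at Week 52, exactly the 2.2.2 rule.

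**Illustration on assumed values only.** Baseline was uniform on 220 to 450, or normal (300, SD 60) truncated to that range. Mean fall was 60, 90 or 110, SD of change 70 or 90, Week 26 to Week 52 correlation 0.3 or 0.6, with no missing data and one million subjects per setting. Across the 24 settings, treating the list as exhaustive:

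- 8.0 to 13.4% of all subjects were counted as in remission with a Week 52 CDAI of 150 or more; these were 24 to 58% of those counted.
- 1.6 to 5.4% of all subjects had a Week 52 CDAI below 150 but were missed.

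**The case against.** The strongest reply is that the SAP often uses 'responder' to mean success on whichever endpoint is being analysed. Section 6.1.5 explains a subject assumed not to be in remission at Week 26 as a non-responder. Sections 6.3.2.3 and 6.3.3.2 do the same for durable and sustained remission, and 6.3.2.2 itself describes its summary output in terms of response. On that usage the two groups reproduce the 2.2.2 rule without error, as shown above. The opening sentence of 6.3.2.2 points the same way. So does the implausibility of a rule that would drop the late remitters the trial expects to see. Section 6.3.3.3 can also be read as the same template applied to a different endpoint. Finally, a list of whom the group will include need not be exhaustive, so the omission of true remitters is conditional.

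Most of this stands, and it makes a drafting slip the likely explanation. It does not remove the conflict. The loose usage concerns 'non-responder'; no section says that 'responder' means CDAI <150. The only formal definition of response is the 100-point one, in force in the paragraph directly above. The possibility of counting subjects with CDAI of 150 or more does not depend on the list being exhaustive.

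A reader might go further and infer that the Week 52 endpoint is really response, or that the rank 3 test loses a calculable amount of power. The documents support neither. The first group requires CDAI <150, and 2.2.2 and 6.1.2 are explicit. No Week 52 rates, CDAI changes, standard deviations or correlations are given from which a power loss could be worked out.

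**Conclusion.** The conflict is real and lies in the second group of 6.3.2.2, not in the endpoint as a whole. Read with response as 2.2.2 defines it, the text admits subjects with a Week 52 CDAI of 150 to 350 whenever baseline is 250 or more. Read also as exhaustive, it leaves out Week 26 responders who reach remission later. Read generically, it agrees with 2.2.2 for every subject.

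The exact results rest only on the SAP's definitions and the eligible baseline range. The simulated percentages rest on assumed distributions, apply only to the literal reading and are not trial estimates; they say nothing about the treatment difference. The point merits correction because the endpoint is rank 3 and gates ranks 4 to 6. The primary endpoint, its sample size and its power are untouched.

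**What to change.** Replace the second sentence of SAP 6.3.2.2 with:

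> A subject is in remission at Week 52 if the Week 52 CDAI is <150, as defined in 2.2.2, whatever the Week 26 status; missing Week 52 CDAI is not in remission, and the treatment-failure and discontinuation rules of 2.2.1, 6.1.5 and 6.1.8 apply.

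The cross-references are needed. A bare CDAI rule would appear to override the failure rules for rescue treatment and early discontinuation, and so create a new conflict. If late remitters are of interest (not in remission at Week 26, in remission at Week 52), tabulate them by arm descriptively only.

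The cost is one sentence, plus one descriptive table if wanted, with no change to data collection or design. It should be made before unblinding, which is the limit SAP 6.8 sets for changes.
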